Exercise training is a proven effective treatment for patients with PAD with significant functional, psychosocial and economic benefits. In current practice, there are no guidelines for exercise training and rehabilitation for patients who have progressed to CLI and have undergone revascularization. While it may be a challenge given the severity of disease and number of comorbidities in this patient population, it is great a disservice to deny these patients exercise rehabilitation given the possible advantages for their functional capacity, quality of life and even survival. Randomized controlled trials (RCT) are necessary to determine the precise role of exercise rehabilitation in patients with CLI. An RCT will provide guidance for regarding exercise tolerance, appropriate exercise modalities as well as the challenges and benefits of exercise rehabilitation in this critically ill population.

Objectives:

The aim of this pilot study is to develop a better understanding of the role for supervised exercise rehabilitation programs (SEP) in CLI patients after revascularization.

Our key objectives are as follows:

- 1) Our primary objective is to show that a 12-week SEP will improve functional capacity and quality of life in patients with CLI after revascularization. We will assess the feasibility for completion of a 12-week SEP in patients with CLI who have undergone revascularization.
- 2) Our secondary objective is to monitor major adverse limb events (MALE) and survival in patients who complete a 12-week SEP after revascularization.

Hypotheses:

- 1) We hypothesize that PAD-CLI patients who participate in an exercise rehabilitation after they have undergone revascularization will have a greater improvement in functional capacity and quality of life compared with patients treated with best medical therapy alone.
- 2) We hypothesize that PAD-CLI patients who participate in an exercise rehabilitation after they have undergone revascularization will have fewer MALE and improved survival compared with patients treated with best medical therapy alone.

OUTCOME MEASURES:

Primary outcome measures:

Our primary outcome measure for this project will be change in functional capacity as measured by a 6-minute walking test (6MWT) or maximal pain-free walking distance on a treadmill.

Secondary outcome measures:

- 1) Quality of life based on questionnaires validated for patients with PAD, the SF-36 and VQ6
- 2) Completion of a 12 week supervised exercise program

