- 2) Freedom from MALE
- 3) Target vessel and/or bypass patency
- 4) Survival at 1, 3 and 5 years

STUDY DESIGN

This study is a two phase, single-center, non-blinded randomized controlled trial. The first phase of the trial will include 20 patients; 10 assigned to post-operative exercise rehabilitation and 10 to best medical therapy. The primary objective of Phase I is to assess for feasibility and safety of this randomized controlled trial in CLI patients after revascularization. We will assess rate of enrollment, adherence to the exercise regimen and any unforeseen barriers or challenges that patients may encounter with the rehabilitation program.

If Phase I of the trial confirms that the exercise program is feasible and safe for CLI patients post-revascularization, we will proceed with Phase II of the trial. The primary objective for Phase II is to determine if a supervised exercise rehabilitation program will improve walking distance after revascularization compared with patients treated with best medical therapy. Phase II will also compare quality of life outcomes between the two groups.

STUDY POPULATION

The population to be studied in this group is patients with PAD and CLI Fontaine classification III and IV. This means that these patients will have ischemic rest pain in their legs and/or non-healing ischemic ulcers on their feet.

ENROLLMENT

Patients will be identified on a referral basis through our outpatient vascular surgery clinic. The seven practicing vascular surgeons in Calgary will be informed of the current study. Patients who have undergone revascularization for CLI will be identified for consideration of participation in this study within six months of their procedure. All surgical and ischemic wounds to be deemed sufficiently healed prior to assessment for fitness in the study. Once the attending vascular surgeon considers the patient fit to participate, the research coordinator will assess the patient for possible inclusion in the study.

Inclusion Criteria

- 1) Ambulating prior to procedure
- 2) Living independently prior to procedure
- 3) Available to attend all SEP and follow-up appointments
- 4) PAD Fontaine class III and IV (rest pain and tissue loss)
- 5) Entry with consent of vascular surgeon
- 6) Ischemia secondary to TASC A-D lesions identified on imaging (CTA or angiogram)
- 7) Able to understand and sign informed consent
- 8) >18 years of age

Exclusion Criteria

- 1) Confined to wheelchair

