- 2) Patients with exercise tolerance limitations due to other co-morbidities such as cardiorespiratory, musculoskeletal, or peripheral neuropathy. (NYHA class III and IV)
- 3) PAD Fontaine class I and II (asymptomatic, claudication)
- 4) Patients with ongoing tissue loss that limits ambulation
- 5) Patient with previous revascularization procedures
- 6) Patients undergoing revascularization for acute limb ischemia events

SAMPLE SIZE

There are currently no data evaluating outcomes of post-revascularization supervised exercise programs in patients with critical limb ischemia, however these studies have been completed in claudication

patients. Studies on PAD claudication (Fontaine class II) patients who have undergone revascularization followed by SEP have all shown significant improvement in functional capacity compared with best medical therapy alone. These previous studies that showed consistently a 20% greater increase in walking distance in the post-revascularization SEP group compared with Best Medical Therapy (BMT) post-revascularization. Given this previous data, 64 patients are required to have a 80% chance of detecting, with a two-sided significance of 0.05, an increase in the primary outcome measure of a 20% greater increase in distance for the 6MWT in the experimental group compared with the control group. Final sample size will be adjusted for expected attrition.

METHODS

INTERVENTION

Patients included in the study will be identified in the vascular surgery outpatient clinic or through Emergency department as requiring revascularization secondary to critical limb ischemia. Patients will be approached regarding study participation prior to the revascularization procedure. After eligibility is confirmed and patients have signed informed consent, patients will be randomized to one of two groups:

- 1) Best Medical Therapy (BMT)
- 2) BMT + Supervised Exercise Program (SEP)

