Microsoft Excel will be used to generate a block randomization sequence for Phase I (20 patients) followed by a block randomization sequence for Phase II (44 patients) of the study. Patients who are eligible to participate in the study will be stratified by sex and randomized to either SEP or BMT. Block sizes of 4 and 6 will be used to prevent anticipation of the randomization sequence.

ALLOCATION CONCEALMENT

Once the random block sequence has been generated, allocation cards will be created and sealed in sequentially numbered opaque envelopes. The envelopes will be stored in a secured filing cabinet in the vascular surgery research office. The envelopes will be opened sequentially after a patient consents to participate in the study.

DATA COLLECTION

No study data will be collected until patients have reviewed and signed the informed consent. Opportunity to ask questions and have time independent from study team will be provided.

Data will be recorded using Excel spreadsheets. Medical outcomes and complications will be tracked using Vascubase software. Data will be stored on Alberta Health Services computers to maintain patient confidentiality.

STATISTICAL ANALYSIS

Normally distributed data will be presented as mean \pm SD. Results at baseline and 12 weeks will be compared using a paired t-test. For data that is not normally distributed, comparisons will be performed using a non-parametric Mann-Whitney test. Comparisons will be accepted as statistically significant at 95% confidence level ($p \leq 0.05$). STATA software will be used for statistical analysis.

ETHICAL CONSIDERATIONS

Patients who are randomized to the SEP group will be provided with tri-weekly visits for supervised exercise guidance and support. Patients will receive reimbursement for travel to and from the exercise facility. This will include refunds for gas, parking or other required transportation (taxi, public transport, etc).

FOLLOW UP OF PATIENTS WITHDRAWN FROM STUDY

Patients who withdraw or do not complete the program will be contacted and interviewed at the end of the 12 week study period to understand why they were unable to complete the training program.

LIMITATIONS

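### No planned analysis uses the baseline walk as a covariate; compared with ANCOVA, a change-score comparison would lose about 6 to 16 of the 64 patients at an assumed correlation of 0.8 to 0.5

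*Combined protocol and SAP*

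**What the plan says.** Under Outcome Measures the primary outcome is given as: "Our primary outcome measure for this project will be change in functional capacity as measured by a 6-minute walking test (6MWT". Pain-free treadmill distance is named as an alternative measure. Whether change means metres or percent is not stated. Under Pre/Post Testing, walking is measured at the first exercise session and again after 12 weeks. QoL questionnaires and ABI are also recorded at the start and at the end.

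The Statistical Analysis section reads: "Normally distributed data will be presented as mean \pm SD. Results at baseline and 12 weeks will be compared using a paired t-test". For non-normal data it substitutes a Mann-Whitney test. It contains no regression model, covariate, adjusted difference or confidence interval for a difference. Under Randomization, stratification is by sex only, so the design does not balance walking ability either.

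Study Design gives Phase II the aim of comparing walking distance between SEP and BMT. Sample Size frames the target the same way, as "a 20% greater increase in distance for the 6MWT in the experimental group compared with the control group".

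**The concern.** A paired t-test is a within-patient comparison and does not answer the Phase II question. The obvious repair is a two-sample test on the changes, but that still uses the baseline inefficiently. A change score subtracts the whole baseline (weight 1), whereas the best weight is the regression slope of the 12-week value on baseline, which is below 1 unless r is high or variance grows. The change score therefore carries avoidable noise, and it over-corrects when one arm happens to start with better walkers.

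At stake is precision in a trial of 64, using a measurement that is already planned. The trial is also described as a pilot for a broader trial. Mean and SD at each visit do not recover the SD of change or the baseline-to-12-week correlation, and the next trial needs both.

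**Working it through.** **Inputs from the protocol.** Total 64, being 20 in Phase I plus 44 in Phase II (Randomization); 80% power and two-sided 0.05 (Sample Size: "64 patients are required to have a 80% chance of detecting, with a two-sided significance of 0.05"); 10 and 10 in Phase I (Study Design), taken here as 1:1 throughout, so 32 per arm.

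**Not in the protocol.** The SD of 6MWT or of its change, and r. I assume r = 0.5 to 0.8, with equal variance s² at both visits.

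**The plan's own figure.** The 64 cannot be reproduced, because a 20% difference without an SD does not fix a sample size. Working backwards, 32 per arm implies a standardised difference of (1.960 + 0.842) × √(2/32) = 0.70 (0.71 with the t distribution). If the effect is 20 percentage points, the implied SD is 20/0.70 = about 28.6 points. An SD of 25, 30 or 40 points would need 50, 72 or 126 patients.

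**Change score against ANCOVA.** Per-patient variances:

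- change score: 2s²(1−r)
- ANCOVA: s²(1−r²)
- ratio: (1−r²)/[2(1−r)] = (1+r)/2

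If a between-arm test on change needs 64, ANCOVA needs 64(1+r)/2. The loss out of 64 is 64(1−r)/2. The number a change-score analysis must add to 64 to match ANCOVA on 64 is 64[2/(1+r) − 1]. Power is for 32 per arm, with the 0.70 divided by the square root of the ratio.

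| r (assumed) | Ratio | ANCOVA needs | Lost out of 64 | Added to 64 | Power if change score has 80% |
|---|---|---|---|---|---|
| 0.5 | 0.75 | 48.0 | 16.0 | 21.3 | 89.9% |
| 0.6 | 0.80 | 51.2 | 12.8 | 16.0 | 87.9% |
| 0.7 | 0.85 | 54.4 | 9.6 | 11.3 | 86.0% |
| 0.8 | 0.90 | 57.6 | 6.4 | 7.1 | 84.0% |

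Outside that range, r = 0.4 gives a loss of 19.2 and r = 0.9 a loss of 3.2.

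**Chance imbalance.** At 32 per arm the standard error of the baseline difference is √(2/32) = 0.25 SD. With an imbalance of that size and r = 0.6, the change score is off by (1 − 0.6) × 0.25 = 0.10 SD. On the same scale the detectable difference is 0.71 × √[2(1 − 0.6)] = about 0.64 SD, so the error is about 16% of it.

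**Unequal variances.** If the 12-week SD is 1.2 times the baseline SD, ANCOVA variance is 1.44(1−r²) and change-score variance is 1 + 1.44 − 2.4r.

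- r = 0.5: 1.08/1.24 = 0.87, a gain of about 13%.
- r = 0.8: 0.518/0.520 = 0.997, almost no gain.

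**The case against.** The strongest objection is that the comparator is not in the plan. No between-arm test of change is written for normally distributed data, so the power figures describe a repair the sponsor might make, not the analysis it has specified. That stands. The missing between-arm primary analysis is the more basic gap, and one sentence specifying ANCOVA closes both.

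Three further points stand and limit the claim:

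- Defining the outcome as a change is not itself an error. Regressing change on arm and baseline gives the same arm effect as regressing the 12-week value on arm and baseline. The deficiency lies in the Statistical Analysis section.
- Lost precision and chance imbalance are one cost, not two. The extra variance, 2(1−r) − (1−r²) = (1−r)², is exactly the imbalance term. Under randomisation the change score is unbiased over repeated trials; the 0.10 SD error is conditional on one imbalanced draw.
- The ratio (1+r)/2 applies to absolute change. The wording of the sample-size target could mean percent change, for which it does not hold.

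Timing is a real difficulty for the fix. The Intervention section has patients consented and randomised before revascularisation, while the walk is taken at the first exercise session. On that reading the baseline is measured after randomisation in an unblinded trial, and BMT patients have no defined equivalent visit. The Enrollment section instead describes identifying patients after the procedure. This does not favour the change score, which depends on the same baseline, but it means that the analysis wording alone is not enough.

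Finally, Phase I is for feasibility and safety, so the precision argument carries weight mainly for the 64-patient comparison.

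**Conclusion.** The point holds as a low-cost improvement. Nothing in the plan adjusts for the baseline walk. Relative to a between-arm comparison of absolute change, that would forgo the equivalent of about 16 to 6 of the 64 patients, or 21 to 7 patients added to 64. This rests on an assumed r of 0.5 to 0.8, equal variances at both visits, 1:1 allocation and 64 analysed patients. At r = 0.8 with growing variance the gain nearly vanishes.

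A reader might infer three stronger things:

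- **That more than a quarter of the sample is wasted.** That needs r below 0.5, since 64(1−r)/2 exceeds 16 only there, and the documents give no r. The larger added-to-64 figures must not be read as losses out of 64.
- **That the protocol prescribes a raw change score in metres.** It says only change, without a scale.
- **That the trial's result would be biased.** Randomisation protects a between-arm change score from that; what is lost is precision.

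**What to change.** In the Statistical Analysis section, state the primary estimate as the SEP minus BMT difference in 12-week 6MWT, in metres, with a 95% CI, from a linear model with arm, baseline 6MWT and sex (the stratification factor). Use the matching baseline value for treadmill distances, QoL scores and ABI. Report the SD of change and the baseline-to-12-week correlation for the broader trial.

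State that the baseline walk is taken at the same defined time point in both arms, before any supervised session. Reconcile the Enrollment, Intervention and Functional Capacity text on when patients are enrolled, randomised and first tested.

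The cost is one or two degrees of freedom (one costs under 2% in variance at this size), slightly more analysis work, and a defined baseline visit for BMT patients. No new measurement is added.

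### The primary outcome is the 6MWT or treadmill distance in the outcome section but the 6MWT alone in the sample size, QoL is ranked both primary and secondary, and no section says the 6MWT alone decides

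*Combined protocol and SAP*

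**What the plan says.** **Walking measure.** Under OUTCOME MEASURES, the primary outcome is "change in functional capacity as measured by a 6-minute walking test (6MWT) or maximal pain-free walking distance on a treadmill". No rule for choosing between the two is given. Under PRE/POST TESTING (Functional Capacity), the tests are not alternatives for different patients: the 6MWT is described first, and patients also do a graded treadmill test. The treadmill test yields two separate measures, maximum walking distance (MWD) and pain-free walking distance (PFWD). The outcome section's wording matches neither label exactly. The SAMPLE SIZE section is written for one measure, "an increase in the primary outcome measure of a 20% greater increase in distance for the 6MWT in the experimental group", with 64 patients, 80% power and two-sided 0.05.

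**QoL.** The Objectives section says "Our primary objective is to show that a 12-week SEP will improve functional capacity and quality of life". LONG-TERM FOLLOW-UP again sets QoL beside functional capacity as a primary endpoint at 12 weeks. The list of secondary outcomes, however, begins with "Quality of life based on questionnaires validated for patients with PAD, the SF-36 and VQ6". Hypothesis 1 joins the two without ranking them: patients in the exercise arm "will have a greater improvement in functional capacity and quality of life compared with patients treated with best medical therapy alone".

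**Phases.** STUDY DESIGN gives Phase I its own aim: "The primary objective of Phase I is to assess for feasibility and safety of this randomized controlled trial". For Phase II it says "The primary objective for Phase II is to determine if a supervised exercise rehabilitation program will improve walking distance after revascularization", and then "Phase II will also compare quality of life outcomes between the two groups".

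**Analysis.** STATISTICAL ANALYSIS names no primary outcome, no order of testing and no multiplicity rule. It accepts comparisons as significant at p ≤ 0.05. For normally distributed data the only test it names is a paired t-test of baseline against 12 weeks.

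**The concern.** Phase II is a powered efficacy comparison, and its power and significance level were set for one measure. With the outcome section as it stands, either walking test could be reported as primary and the protocol cited in support. Two things follow.

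First, if the 6MWT and the treadmill disagreed, the outcome section would not say which one answers the Phase II question. The Phase II objective does not help, because walking distance describes either test.

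Second, if either test could count, or the test were chosen after the results were known, the chance of a false-positive claim would exceed the stated 5%. The trial is not blinded, so a late choice could be made with the results by arm in view. The double ranking of QoL adds a further possible route to a primary claim.

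**Working it through.** **1. The sections side by side**

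| Section | Walking measure | QoL |
|---|---|---|
| Objectives | functional capacity, no test named | primary |
| Hypothesis 1 | functional capacity, no test named | joined, unranked |
| OUTCOME MEASURES | 6MWT *or* treadmill | secondary |
| STUDY DESIGN, Phase II | walking distance, no test named | additional |
| SAMPLE SIZE | 6MWT only | not mentioned |
| PRE/POST TESTING | 6MWT, and also treadmill (MWD, PFWD) | measured, unranked |
| STATISTICAL ANALYSIS | none named | none named |
| LONG-TERM FOLLOW-UP | functional capacity, no test named | primary |

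Only SAMPLE SIZE ties the word primary to the 6MWT alone.

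**2. The plan's own figure.** RANDOMIZATION gives 20 patients in Phase I and 44 in Phase II, and 20 + 44 = 64, so 64 is the total. That is 32 per arm at 1:1 (stated for Phase I, assumed for Phase II). No SD, baseline mean or control-arm change is given, so 64 cannot be reproduced. Working backwards with the normal approximation:

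d = (1.960 + 0.842) × √(2/32) = 2.802 × 0.25 = 0.70.

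If the 20% effect means 20 percentage points, the implied SD is 20/0.70, or about 28.6 points. SDs of 25, 30 and 40 would give totals of 50, 72 and 126. The figure is neither confirmed nor refuted, and the point does not depend on it.

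**3. Error rate if either of two walking measures could count.** Assume a valid between-arm test of each measure at two-sided 0.05, no true effect, and test statistics with correlation r. Then

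false-positive rate = 1 − P(|Z₁| ≤ 1.96 and |Z₂| ≤ 1.96).

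At r = 0 this is 1 − 0.95² = 9.75%. The other values come from the bivariate normal distribution. The documents give no correlation, so the range is assumed.

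| r | 0 | 0.3 | 0.5 | 0.7 | 0.8 | 0.9 |
|---|---|---|---|---|---|---|
| Two measures | 9.75% | 9.51% | 9.07% | 8.35% | 7.81% | 7.04% |
| Three measures | 14.3% | 13.6% | 12.6% | 11.0% | 9.8% | 8.4% |

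The second row applies if the 6MWT, MWD and PFWD all counted, or two walking measures and one QoL score. At r = 0 it is 1 − 0.95³ = 14.3%; the rest are simulated with equal pairwise correlation.

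**4. Error rate if the 6MWT alone decides.** In 100,000 simulated null trials per setting, with 32 per arm and an assumed baseline-to-12-week correlation of 0.7, ANCOVA on the 6MWT gave 5.0% to 5.1%. There is also no inflation if every measure must succeed.

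**The case against.** The strongest reply is that the documents already settle the ranking. SAMPLE SIZE, the only section that sets significance level and power, uses the 6MWT. The methods describe the 6MWT first and add the treadmill test. The Phase II design and the outcome list both put walking above QoL. On this view one loose conjunction and some loose wording on QoL remain. Much of this stands: the lean is real, and it lowers the severity. It does not remove the conflict, because the section whose job is to define the primary outcome allows either test, and nothing says that the sample-size sentence prevails.

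A reader might infer that the plan lets success be declared on either test and so runs a false-positive rate near 10%. The documents do not support that. The *or* describes how functional capacity is measured; no success rule is stated. The rates above therefore depend on a rule that the plan does not contain. They are not the error rates of STATISTICAL ANALYSIS as written, whose paired test does not compare the arms. Zero correlation between two walking tests in the same patients is also an extreme case.

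It may be said that the missing between-arm test is a separate matter and that hypotheses do not rank outcomes. Both are fair. Hypothesis 1 can stay as it is. A statement of which result decides still needs a test that compares the arms, so the two repairs are best made together.

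Finally, this is called a pilot, and a broader trial is planned. That limits the consequences, but Phase II is powered for an efficacy question.

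**Conclusion.** The inconsistency is real. The primary outcome is one of two walking tests in one section and the 6MWT alone in another. QoL is primary in two places, secondary in one and additional in another. The text leans to the 6MWT without saying that it alone decides.

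The size is conditional. If either of two walking measures could count, the false-positive rate would be 7.0% to 9.8% instead of 5%. With three measures it would be about 8.4% to 14.3%. Both ranges assume correlations from 0.9 down to 0 and valid between-arm tests at 0.05. If the 6MWT alone decides, there is no inflation.

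This should be resolved before any outcome data are compared, because prespecification cannot be restored once both results have been seen. Given the lean to the 6MWT, it is a clarification the sponsor should make and not a fault that undermines the design.

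**What to change.** 1. **OUTCOME MEASURES:** name the between-arm difference in change in 6MWT distance from baseline to 12 weeks as the single primary efficacy outcome, tested at two-sided 0.05, as SAMPLE SIZE assumes.
2. **Secondary outcomes:** list treadmill PFWD and MWD there, under the labels used in PRE/POST TESTING.
3. **QoL:** make it secondary in the primary objective and in LONG-TERM FOLLOW-UP. Hypothesis 1 may stay. Leave the Phase I feasibility and safety objectives unchanged.
4. **STATISTICAL ANALYSIS:** state that efficacy is judged on a between-arm test of the 6MWT, for example ANCOVA adjusted for baseline 6MWT, and that other comparisons are secondary.

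The cost is rewording in these sections and one added analysis; no new measurement is needed. Removing the *or* gives no reason to change the planned 64, although 64 itself cannot be verified without an SD and a scale for the 20% effect. The sponsor gives up the option of claiming primary success on treadmill distance or QoL.

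Keeping two chances of success with a Bonferroni split (0.025 each) would cost more. At the back-calculated d = 0.70, power at 64 falls to about 71%, and 78 patients would be needed for 80%.

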Functional Capacity:

In order to assess functional capacity, we will measure walking performances at the first exercise session and after 12 weeks. Walking performance will be measured using a six-minute walk test (6MWT) (Guyatt et al, 1985) which has been validated in the functional evaluation of chronic disabling disease, more specifically in patients with PAD (Gardner, Montgomery, & Parker, 2012; McDermott et al., 2009). For this test, the patients will be made to walk on a flat surface for 6 minutes and total distance covered will be recorded by the test administrator. Patients will also undergo a graded treadmill test to evaluate maximum walking distance (MWD) and pain-free walking distance (PFWD). The treadmill is set at a constant speed of 3.2km/hr and starts at an incline of 0%, increasing by 2% every 2 minutes until an incline of 10% is reached or the patients stops the test (Gardner et al., 2012). This test is also commonly used and has been validated in PAD patients.

Quality of Life (QoL):

Validated generic and PAD-specific QoL questionnaires will be administered at the first and final visits. The Short Form 36 (SF-36) and VascuQol. The SF-36 is a generic health status questionnaire, while the VascuQol is a quality of life questionnaire validated for patients with PAD.

Given that this is a pilot study to assess the feasibility in exercise rehabilitation in this population that is considered end-stage PAD, we want to capture major challenges or barriers for these patients. As such, we will also perform an interview and survey at the mid-term and at the completion of exercise program for the SEP group to collect information around challenges associated with the rehabilitation.

Limb Hemodynamics:

Ankle brachial index (ABI) measurements will be recorded at initial assessment and 12 weeks as a measure of peripheral arterial blood flow. ABI is obtained by measuring the highest systolic pressure at the ankle over the highest systolic pressure in the arm. We will use a handheld Doppler probe and blood pressure cuff to collect these measurements. We will also use duplex arterial ultrasound at 2 weeks post intervention and again at 12 weeks to monitor patency of revascularization.

RANDOMIZATION

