One expected limitation of this study is the heterogeneity of the revascularization approach. Some patients will undergo endovascular treatment, while others will receive an open surgical bypass. Additionally, patients will not be stratified according to anatomical level of disease (aorto-iliac versus infrainguinal disease).

LONG-TERM FOLLOW-UP

This project is a pilot project with 12-week primary endpoint measures of functional capacity and quality of life. Given that we plan to extend to a broader randomized controlled clinical trial with long term follow-up, we will continue to follow the patients annually for five years. The annual follow-up will include QoL surveys, ABI measurements, ultrasound assessment for graft patency and any MALE. We will also monitor survival throughout this period.

REFERENCES

Adam, D. J., Beard, J. D., Cleveland, T., Bell, J., Bradbury, A. W., Forbes, J. F., . . . Storkey, H. (2005). Bypass versus angioplasty in severe ischaemia of the leg (BASIL): multicentre, randomised controlled trial. *Lancet*, 366(9501), 1925-1934. doi:10.1016/s0140-6736(05)67704-5

Agarwal, S. (2009). The association of active and passive smoking with peripheral arterial disease: results from NHANES 1999-2004. *Angiology*, 60(3), 335-345. doi:10.1177/0003319708330526

Badger, S. A., Soong, C. V., O'Donnell, M. E., Boreham, C. A., & McGuigan, K. E. (2007). Benefits of a supervised exercise program after lower limb bypass surgery. *Vasc Endovascular Surg*, 41(1), 27-32. doi:10.1177/1538574406296209

Bavry, A. A., Anderson, R. D., Gong, Y., Denardo, S. J., Cooper-Dehoff, R. M., Handberg, E. M., & Pepine, C. J. (2010). Outcomes Among hypertensive patients with concomitant peripheral and coronary artery disease: findings from the INternational VErapamil-SR/Trandolapril STudy. *Hypertension*, 55(1), 48-53. doi:10.1161/hypertensionaha.109.142240

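### No single quality-of-life score is chosen to decide hypothesis 1, and every comparison counts at p ≤ 0.05, so a QoL benefit could be claimed from whichever score crosses the line

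*Combined protocol and SAP*

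**What the plan says.** All references are to the combined protocol and SAP.

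- **Role of QoL.** Under Objectives: "Our primary objective is to show that a 12-week SEP will improve functional capacity and quality of life in patients with CLI after revascularization". Hypothesis 1 predicts a greater QoL improvement with exercise than with best medical therapy alone. STUDY DESIGN plans a between-group QoL comparison in Phase II. LONG-TERM FOLLOW-UP counts QoL among the 12-week primary endpoint measures, although OUTCOME MEASURES lists it as secondary.
- **Instruments.** The secondary outcome is "Quality of life based on questionnaires validated for patients with PAD, the SF-36 and VQ6". PRE/POST TESTING names "The Short Form 36 (SF-36) and VascuQol" and adds: "The SF-36 is a generic health status questionnaire, while the VascuQol is a quality of life questionnaire validated for patients with PAD". The label VQ6 is not explained and does not recur.
- **Timing.** "Validated generic and PAD-specific QoL questionnaires will be administered at the first and final visits". After 12 weeks, "The annual follow-up will include QoL surveys, ABI measurements, ultrasound assessment for graft patency and any MALE", for five years.
- **Testing.** STATISTICAL ANALYSIS says "Results at baseline and 12 weeks will be compared using a paired t-test", with a Mann-Whitney test for non-normal data. It then says "Comparisons will be accepted as statistically significant at 95% confidence level", with p ≤ 0.05 as the threshold. It gives no key QoL score, testing order or multiplicity adjustment.

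**The concern.** Half of hypothesis 1 rests on QoL, yet the plan does not say which number decides it. Two questionnaires give at least two scores, and more if domains or summaries are analysed. Each may be declared significant on its own at p ≤ 0.05. After the data are seen, any one of them could be presented as the QoL result. The trial is non-blinded and these questionnaires are self-reported, so naming the deciding score in advance is one of the few safeguards available.

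A smaller matter adds to this. The PAD-specific questionnaire has one label in the outcome list and another in the testing section, neither with a version. The annual visits refer only to QoL surveys. Someone running the trial cannot tell from the text exactly which form is meant.

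**Working it through.** **The plan's own figure.** There is no QoL sample size, power or error rate to reproduce. The stated 64 patients (20 in Phase I plus 44 in Phase II, about 32 per arm) concern the 6MWT only. No SD is given, so 64 cannot be reproduced. With 80% power and two-sided 0.05 it implies a standardized difference of √(2/32) × (1.960 + 0.842) = 0.70. This has no bearing on the QoL point.

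**Inputs.**

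- Threshold per comparison: 0.05 (STATISTICAL ANALYSIS). Read as a two-sided test, 0.025 of that favours the exercise arm (SEP).
- Number of QoL scores, k: not stated. Two questionnaires with one score each give k = 2, the least the text supports.
- Wider range, k = 3 to 11: an assumption, namely 2 to 10 SF-36 scores plus one PAD-specific score.
- Each score is assumed to be compared between arms with a valid test.

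**Independent scores, no true effect.** The chance of at least one significant result is 1 − 0.95^k in either direction. The chance of at least one favouring SEP is 1 − 0.975^k.

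| k | Either direction | Favouring SEP |
|---|---|---|
| 1 | 5.0% | 2.5% |
| 2 | 1 − 0.9025 = 9.75% | 1 − 0.9506 = 4.9% |
| 3 | 1 − 0.8574 = 14.3% | 1 − 0.9269 = 7.3% |
| 10 | 1 − 0.5987 = 40.1% | 1 − 0.7763 = 22.4% |
| 11 | 1 − 0.5688 = 43.1% | 1 − 0.7569 = 24.3% |

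**Correlated scores.** Scores from the same patients will usually be positively correlated, which lowers these figures. A simulation used 32 patients per arm, two-sample t-tests, equal correlation between scores and 20,000 runs. Its Monte Carlo standard error is at most about 0.3 percentage points.

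| k | Correlation | Either direction | Favouring SEP |
|---|---|---|---|
| 2 | 0.5 | 8.9% | 4.3% |
| 2 | 0.8 | 7.8% | 4.0% |
| 3 | 0.5 | 12.7% | 6.4% |
| 3 | 0.8 | 9.9% | 5.0% |
| 10 | 0.5 | 29.1% | 14.4% |
| 10 | 0.8 | 17.6% | 8.7% |

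**The test itself.** For normally distributed data the plan names only a paired comparison of baseline with 12 weeks, which is a within-arm test. Patients may improve after revascularization whether or not they exercise, so a significant within-arm change is not evidence for SEP. Naming one score therefore controls the error on hypothesis 1 only if that score is compared between arms.

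**After the change.** One named score, one time point and one between-arm test give 5% two-sided and 2.5% in favour of SEP.

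**The case against.** The strongest reply is that this is a pilot, that QoL is listed as secondary, and that unadjusted secondary outcomes are common when reported as exploratory. STUDY DESIGN does make walking distance the primary objective of Phase II. But the same document places QoL in the primary objective, in hypothesis 1 and among the 12-week primary endpoint measures, and it sets a significance threshold without labelling QoL exploratory. The reply softens the point but does not remove it.

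A second reply concerns size, and it largely stands. The number of scores beyond two is not in the documents, independence is the upper case for positively correlated scores, and two-sided figures count results favouring best medical therapy as well. A reader might take 14% to 43% as the chance of falsely claiming a QoL benefit. The text does not support that: for the same assumed scores the figure favouring SEP is 7% to 24% at most, and for the two scores the text supports it is 4.9%.

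A third reply concerns the instrument. A reader might infer from the two labels that different questionnaires, or different versions, would be used at baseline and at 12 weeks. The documents do not show this. Both sections pair the SF-36 with one other questionnaire described as validated in PAD, and the testing section gives the same pair at the first and final visits. One instrument under two labels is the natural reading. What remains is an unstated version and an unspecified survey at the annual visits.

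**Conclusion.** The point holds as a gap in pre-specification. QoL carries part of the main hypothesis, no score decides it, and nothing limits how many scores may be tested at 0.05.

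From the text alone, with two scores, the excess is moderate: up to 9.75% against 5% two-sided, or 4.9% against 2.5% in favour of SEP. It becomes large only if many scores are tested, which is an assumption. Even then correlation reduces it: for ten scores the two-sided figure is about 29% at correlation 0.5 and 18% at 0.8, against 40% if independent. All these figures also assume valid between-arm tests, which the statistical section does not name for normally distributed data.

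The differing labels are a wording matter to reconcile, not evidence that two scales would be mixed. The remedy is a cheap improvement.

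**What to change.** 1. In OUTCOME MEASURES and STATISTICAL ANALYSIS, name one score of the PAD-specific questionnaire. State that its change from baseline to 12 weeks, compared between arms, is the single QoL test for hypothesis 1 at two-sided 0.05.
2. Report the SF-36 scores, any other QoL scores and the annual QoL visits as between-arm differences with 95% confidence intervals, without significance claims.
3. Use one instrument name and version in OUTCOME MEASURES, PRE/POST TESTING and LONG-TERM FOLLOW-UP.

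Testing QoL only after a significant 6MWT result is optional and not part of this fix. It is a decision about the ranking of outcomes, and the primary outcome is itself still worded as either the 6MWT or a treadmill distance. If the sponsor wants a formal claim from each questionnaire, two named scores at 0.025 each would also hold the error (1 − 0.975² = 4.94% if independent).

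The cost is a change of wording in these sections, with no extra patients, visits or data. The sponsor gives up significance claims on the remaining QoL scores.
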